## **Study Protocol with Statistical Analysis Plan**

### **Background/Rationale**

Nosocomial diarrhea is defined as diarrhea that develops after 72 hours of hospitalization. This condition is common among hospitalized patients with reported prevalence of 14-21%. The causes of nosocomial diarrhea can be categorized into inflammatory and non-inflammatory causes. For inflammatory etiologies, the most concern is *Clostridium difficile* infection. Other infections such as cytomegaloviral enterocolitis can also occur because immune function can be suppressed during critical illness. Ischemic enterocolitis is another cause in the inflammatory group. The non-inflammatory causes include adverse effects of medications and tube-feeding diarrhea. Differentiating inflammatory diarrhea from non-inflammatory diarrhea is important. Investigations for distinguishing these two conditions are stool *C. difficile* toxin test and stool examination. Because the reported sensitivity of only 60-70% for *C. difficile* toxin test by EIA method, which is most widely used in many centers, and the diagnosis of CMV is based on pathological findings, inflammatory diarrhea cannot be excluded completely by the negative stool tests. Colonoscopy is still required in some cases. However, although colonoscopy is a low risk procedure, the risk may increase if performed in hospitalized patients, who may have many comorbidities. A noninvasive test that can better differentiate inflammatory from noninflammatory diarrhea could help physicians to perform colonoscopy more appropriately. Calprotectin is a protein found in human neutrophils, and it is released during active periods of inflammation of intestine. The sensitivity and specificity has been reported at 93% and 96%, respectively in differentiating inflammatory bowel disease from irritable bowel syndrome in outpatient setting. Hence, its benefit in differentiating inflammatory from noninflammatory diarrhea in nosocomial diarrhea is possible, but never been studied. In the present study, we aim

to study the efficacy of fecal calprotectin in distinguishing inflammatory nosocomial diarrhea from non-inflammatory nosocomial diarrhea. Furthermore, the level of fecal calprotectin has been reported to be associated with the degree of intestinal inflammation. It could have a role in determine prognosis of the patients.

## **Study design**

The study is a prospective observational study performed at tertiary care center from June 2019 to June 2020.

## **Population**

### **1. Sample size**

In literature review, we found a study comparing fecal calprotectin levels between *C. difficile* associated diarrhea and antibiotic associated diarrhea. The median fecal calprotectin level in *C. difficile* associated diarrhea was 684.8 (range:203.7 to 1581.0) and the median level in antibiotic associated diarrhea was 66.5(range :23.1 to 145.7). Using Mann-Whitney U test with a standard normal of 1.96, alpha error of 5%, and power of 80%, the calculated sample size is 61patients in each group.

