#### ***The inflammatory diarrhea is defined if***

- 1) positive for *C. difficile* toxin or
- 2) stool WBC more than 5/HPF or
- 3) inflammatory mucosa or ulceration noted on colonoscopy

[figure not shown]

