## Outcome Measures

Primary outcome: To determine the efficacy of fecal calprotectin in distinguishing inflammatory nosocomial diarrhea from non-inflammatory nosocomial diarrhea.

Secondary outcome: Correlation of fecal calprotectin levels and prognosis of hospitalized patients with nosocomial diarrhea.

The participants with nosocomial diarrhea were tested for C.difficile and stool examination or further colonoscopy for definite diagnosis group of diarrhea. Their leftover specimens will be kept until the end of the study. Then all collected stool specimens will be measured for calprotectin levels. Overall data collected of 147 participants will be completed analyzed about August 2020.

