### **Limitations and Caveats**

1. Some participants cannot undergo colonoscopy for definite diagnosis of nosocomial diarrhea due to risk of procedures. These patients will be excluded from the study.

2. Number of participants in two groups were not equal as this is an observational study.

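### The 61 patients per group cannot be reproduced from the medians, ranges and 80% power the plan attributes it to; an unstated input must have been used

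*Combined protocol and SAP*

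**What the plan says.** The calculation is one short paragraph in the combined protocol and SAP, under Population, "1. Sample size". It takes its effect from a published comparison of *C. difficile* diarrhea with antibiotic-associated diarrhea, giving the median calprotectin levels and limits as "684.8 (range:203.7 to 1581.0) and the median level in antibiotic associated diarrhea was 66.5(range :23.1 to 145.7". The method is described as "Using Mann-Whitney U test with a standard normal of 1.96", with "alpha error of 5%, and power of 80" (per cent). The result is that "the calculated sample size is 61patients in each group".

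The paragraph gives no SD, no P(X>Y), no rule for turning the limits into a variance, no formula, and no allowance for attrition or for a smaller effect. The plan has no other justification of its size.

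**The concern.** The two ranges do not overlap: the lowest *C. difficile* value (203.7) is above the highest antibiotic-associated value (145.7). In the cited sample every patient in one group therefore exceeds every patient in the other. A rank test needs only a handful of patients to detect that, so 61 per group at 80% power looks out of line with its own inputs.

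At stake is whether a reader can tell what effect the study was sized to detect. The primary outcome is discrimination, analysed with an ROC curve, so the AUC detectable with 61 per group is the useful figure, and the plan does not give it.

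**Working it through.** **Inputs, all from "1. Sample size".** Difference in medians 684.8 − 66.5 = 618.3. Widths of the limits 1581.0 − 203.7 = 1377.3 and 145.7 − 23.1 = 122.6. The pairing of 1.96 with a 5% alpha means a two-sided test. Power 80%, equal groups. So (1.960 + 0.842)² = 7.849.

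**Formulas.**
- Means: n per group = 7.849 × (SD₁² + SD₂²) / 618.3². Dividing by 0.864, the lowest asymptotic efficiency of the Mann-Whitney test relative to the t-test, gives a cautious Mann-Whitney figure.
- Noether, equal groups: n per group = 7.849 / [6 × (P − 0.5)²], where P = P(X>Y), which is also the AUC.

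**Attempt to reproduce 61.** The plan does not say how the limits became a variance, so the plausible conventions were tried in turn.

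| Reading of the limits | SDs | n per group (means formula; then ÷ 0.864) |
|---|---|---|
| True ranges, SD = width/4 | 344.3 and 30.7 | 2.5; 2.8 |
| Same, larger SD in both groups | 344.3 | 4.9; 5.6 |
| True ranges, each group's largest possible SD (half the range) | 688.65 and 61.3 | 9.8; 11.4 |
| Assumed IQRs, SD = width/1.35 | 1020.2 and 90.8 | 21.5; 24.9 |
| Same, larger SD in both groups | 1020.2 | 42.7; 49.5 |
| Full width used as the SD | 1377.3 and 122.6 | 39.3; 45.4 |
| Same, larger SD in both groups | 1377.3 | 77.9; 90.2 |

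Two rows in full:
- Half-range: 7.849 × (688.65² + 61.3²) / 618.3² = 7.849 × 477,997 / 382,295 = 9.8.
- IQR: 7.849 × (1020.2² + 90.8²) / 382,295 = 21.5.

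Starting from the t-test sample size instead of the normal formula raises the 49.5 to 50.6.

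**Noether's formula.**
- Ranges as written, P = 1: 7.849 / (6 × 0.25) = 5.2, so 6 per group.
- IQRs under normality, P = Φ(618.3/√(1020.2² + 90.8²)) = 0.727: about 25.4, so 26 per group.

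The smallest means-formula results should not be taken at face value. With complete separation the exact two-sided p-value is 0.10 at 3 per group and 0.029 at 4, so 4 is the practical minimum. If the limits are IQRs and the data keep the skew that the medians imply, simulated Mann-Whitney power reaches 80% at about 8 to 16 per group.

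No row gives 61.

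**What 61 would require at two-sided 5% and 80% power.**
- P(X>Y) = 0.5 + √[7.849 / (6 × 61)] = 0.646; or
- a common SD of 618.3 × √[61 / (2 × 7.849)] = 1,219 (normal formula), or about 1,122 from the t-test formula with the 0.864 factor; or
- an added allowance, for example 50.6 × 1.2 = 60.7.

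**Power at 61 per group.** By Noether, power = Φ(√(12 × 61 × 61/122) × (P − 0.5) − 1.96) = Φ(19.13 × (P − 0.5) − 1.96).
- Ranges as written, P = 1: Φ(7.6), above 99%.
- IQRs under normality, P = 0.727: Φ(2.38), about 99%.
- IQRs with the larger SD in both groups, P = 0.666: Φ(1.21), about 89%.

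**The case against.** **The limits may be IQRs labelled as ranges.** The plan does not exclude this, and it moves the need from single figures to the twenties. It still does not give 61 without the larger SD in both groups plus a further allowance. IQRs alone guarantee only P(X>Y) ≥ 0.75 × 0.75 = 0.5625, so sufficiently skewed data could be compatible with 0.646. That leaves 61 possible under an IQR reading, but not derived from what is stated.

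**A smaller effect may have been intended.** The inflammatory group here also admits patients with "stool WBC more than 5/HPF" or colonoscopic findings, so it is broader than the cited *C. difficile* group. That would be a sound reason to plan for less separation. The plan does not give it.

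**The replacement figures depend on conventions the plan does not state either.** This stands. Normal distributions with SDs this large put a sizeable share of calprotectin values below zero, so no single figure above should be adopted as the right sample size. A reader might, for example, put the half-range SD of 689 into both groups and report 20 to 23 as the need on the inputs as written. The antibiotic-associated range allows an SD of at most about 61, so the documents do not support that.

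**A reader might infer that 90% power was used by mistake.** With the larger IQR-based SD in both groups, 90% power gives 60.9 under one efficiency correction (t-test n ÷ 0.955). Several other combinations also land near 61, and nothing in the plan points to any of them. Likewise 122 × 1.2 = 146.4, which would round up to the 147 participants named under Outcome Measures, but the plan does not link the two numbers.

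**The consequence is small.** This also stands: no patient number or analysis changes.

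**Conclusion.** The figure of 61 per group is not reproducible from the inputs it is attributed to. Those inputs need about 3 to 6 per group read literally, and at most about 10 to 11 with each group's largest possible SD. On the unstated assumption that the limits are IQRs, the need is about 22 to 26 under normality, fewer with skew, and 43 to 51 only with the larger SD in both groups. The stated 80% power does not describe the cited effect, for which power at 61 exceeds 99% on the ranges as written.

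A reader might go on to infer that the study is underpowered. The documents do not support that. On the literal and IQR readings 61 is more than enough; it falls short only if the full width of the limits is used as the SD in both groups, which the cited range does not allow. Nor do they support calling the study too large, since the study's own inflammatory group is more mixed than the cited one.

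This is a minor point. Confidence is high that 61 does not follow from the stated inputs; it does not extend to any single replacement number.

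**What to change.** In "1. Sample size", stop presenting 61 as derived from the cited medians and ranges at 80% power. Then do one of the following.

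1. Correct the calculation: state the P(X>Y) or SD actually used, the formula, any inflation or attrition allowance, and whether the limits are ranges or IQRs. If a smaller effect was assumed because the inflammatory group is broader than *C. difficile* alone, say so.
2. If those inputs cannot be recovered, say that, and restate the number as an operating characteristic labelled as after the fact: 61 per group gives 80% power, at two-sided 5%, to detect an AUC of about 0.65 versus 0.5.

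The cost is a few sentences, with no additional patients and no change to the analysis. The downside is that, unless the missing input is found, the size can no longer be presented as derived from the cited study, and option 2 describes 61 without justifying it.

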### **2. Study population**

#### Inclusion Criteria:

- 1.Ageat least 18 years
- 2.Diarrhea more than 3 bowel movements per day which develops after 72 hours of admission

#### Exclusion Criteria:

- 1.Intraabdominal pressure more than 12 mmHg
- 2.Patient on chemotherapy with neutropenia (ANC less than 1,000/mm^3)

### **Study procedures**

The patients with nosocomial diarrhea who are tested for *C.difficile* infection and stool examination will be recruited. Their leftover stool specimens about 100mg will be collected and frozen at -80 celsius degree until the end of study. All collected samples will be measured for calprotectin levels.

#### ***The inflammatory diarrhea is defined if***

- 1) positive for *C. difficile* toxin or
- 2) stool WBC more than 5/HPF or
- 3) inflammatory mucosa or ulceration noted on colonoscopy

[figure not shown]

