#### ***The noninflammatory diarrhea is defined if***

- 1) negative for *C. difficile* toxin and
- 2) no WBC on stool examination and
- 3) dramatic and persistent response to diet adjustment

Or

- 4) no mucosal inflammation or ulceration if colonoscopy is performed

The management and enrollment flow chart is shown in Figure 1.

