### **Statistical Analyses**

The continuous data will be reported in mean and standard deviation or median and range as appropriate.

Categorical data will be reported in percentage or frequency.

Comparision of factors and patient characteristic between inflammatory and non-inflammatory diarrhea groups will be analyzed using independent t-test or Wilcoxon Rank Sum test for continuous variables, and chi-square test or fisher exact test for categorical variables.

Fecal calprotectin levels between inflammatory and non-inflammatory diarrhea will be shown in receiver operating characteristic curve(ROC). The best cut off will be calculated.

Correlation of fecal calprotectin levels and treatment outcomes, both univariate and multivariate analysis, will be analyzed by logistic regression.

P value < 0.05 will be considered statistically significant.

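### Stool WBC helps set the reference label while calprotectin is a neutrophil protein from the same stool work-up, so their errors may be shared; the planned AUC is distorted in an unknown direction, and a WBC-free sensitivity ROC is missing

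*Combined protocol and SAP*

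**What the plan says.** - **Inflammatory label (Study procedures).** Three criteria are alternatives: a positive *C. difficile* toxin test, "stool WBC more than 5/HPF or" "inflammatory mucosa or ulceration noted on colonoscopy". A raised stool WBC count is enough alone, with no confirmation by colonoscopy.
- **Non-inflammatory label (Study procedures).** The stool route requires a negative toxin test, "no WBC on stool examination and" a lasting response to diet adjustment. The alternative route is "no mucosal inflammation or ulceration if colonoscopy is performed".
- **Index test (Background/Rationale).** "Calprotectin is a protein found in human neutrophils, and it is released during active periods of inflammation of intestine".
- **Specimen (Study procedures).** The patients recruited are those sent for toxin testing and stool examination. "Their leftover stool specimens about 100mg will be collected and frozen" for the assay at study end. The Data collection process section says the routine microscopy supplies the cell count.
- **Analysis (Statistical Analyses).** One ROC and one best cut-off are planned against these two labels. No analysis uses a label without stool WBC, and the Limitations section does not mention the overlap.

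**The concern.** An ROC analysis measures accuracy only as well as its reference label does. Here a leukocyte count in stool can put a patient in either group, and the test being judged is a neutrophil protein in stool from the same work-up. Anything that raises or lowers neutrophils in the specimen without matching the state of the mucosa can move both readings the same way. Within truly inflamed patients, and within truly non-inflamed patients, the two need not be independent.

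The Background names stool examination as a current test, says negative stool tests cannot fully exclude inflammation, and seeks a noninvasive test that separates the groups better. For patients labelled by WBC, the ROC partly shows agreement with the test that calprotectin is meant to improve on. At stake are the primary AUC, the sensitivity and specificity, and the cut-off chosen from the same curve.

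**Working it through.** **The plan's own figure.** The plan states no expected AUC, so there is none to reproduce. Its 61 per group is used below only as a group size; the point does not depend on how 61 was derived.

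**Two opposing effects.** Let rho be the correlation between calprotectin and latent stool WBC within a true class.

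1. With rho = 0, mislabelled patients dilute both groups and the observed AUC falls below the true one.
2. With rho > 0, patients put in the inflammatory group by WBC tend to have high calprotectin and those admitted through the no-WBC rule tend to have low calprotectin. The observed AUC rises relative to rho = 0.

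**Simulation, first set of inputs.** All inputs are assumptions, because the documents do not give them: 40% truly inflamed; toxin positive in 35% of inflamed patients and independent of calprotectin given class; binormal calprotectin; colonoscopy in 40% of stool-negative and 10% of stool-positive patients; diet response in 60% of non-inflamed and 10% of inflamed. The cut for no WBC on the latent scale is also assumed. Labels follow the protocol's rules. Expected AUC against the planned label:

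| True AUC | WBC sens./spec. | rho 0 | rho 0.3 | rho 0.5 | rho 0.7 |
|---|---|---|---|---|---|
| 0.75 | 50%/85% | 0.69 | 0.76 | 0.80 | 0.85 |
| 0.75 | 30%/95% | 0.72 | 0.76 | 0.79 | 0.81 |
| 0.90 | 50%/85% | 0.81 | 0.86 | 0.90 | 0.93 |

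At a true AUC of 0.97 (WBC 50%/85%) the planned AUC is low throughout, from 0.86 at rho 0 to 0.96 at rho 0.7. The share of the inflammatory group labelled by WBC alone is about 50% in the 50%/85% setting and about 31% in the 30%/95% setting.

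**Second set of inputs, as a check.** Prevalence 30% or 50%; WBC 50%/90%, 70%/80% or 60%/70%; toxin sensitivity 65% (the middle of the 60-70% in the Background, here applied to all inflamed patients) and specificity 97%; diet response in 15% of inflamed and 80% of non-inflamed; half of undetermined patients scoped, without error. Observed minus true AUC:

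| True AUC | rho 0 | rho 0.5 | rho 0.9 |
|---|---|---|---|
| 0.70 | -0.09 to -0.03 | +0.04 to +0.07 | +0.10 to +0.20 |
| 0.80 | -0.14 to -0.04 | +0.01 to +0.03 | +0.08 to +0.13 |
| 0.90 | -0.18 to -0.06 | -0.05 to -0.01 | +0.03 to +0.06 |

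The net bias turns upward at a rho of about 0.3, 0.5 and 0.7 for true AUCs of 0.70, 0.80 and 0.90.

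**With WBC out of the label.** Under the second set the AUC no longer depends on rho. It is about 0.68, 0.77 and 0.86 for true values of 0.70, 0.80 and 0.90, which is 0.02 to 0.04 low, because toxin and diet-response error remain.

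**Precision cost (Hanley-McNeil, A = 0.80, 61 non-inflammatory).** Q1 = A/(2-A) = 0.6667; Q2 = 2A²/(1+A) = 0.7111; A² = 0.64. The variance is [A(1-A) + (n1-1)(Q1-A²) + (n0-1)(Q2-A²)]/(n1·n0).

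- n1 = 61: (0.16 + 60×0.0267 + 60×0.0711)/3721 = 0.00162, SE 0.040.
- n1 = 41 (about one third removed): (0.16 + 40×0.0267 + 60×0.0711)/2501 = 0.00220, SE 0.047.
- n1 = 31 (about one half removed): (0.16 + 30×0.0267 + 60×0.0711)/1891 = 0.00276, SE 0.053.

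**The case against.** A reader might infer that the planned AUC is most likely inflated. The documents do not support that. Inflation depends on the true AUC and on rho, and neither is given. The documents' own figures suggest a high true AUC: the Background cites 93% sensitivity and 96% specificity in outpatients with inflammatory bowel disease versus irritable bowel syndrome, and the two planning ranges in the sample size section (203.7 to 1581.0 and 23.1 to 145.7) do not overlap. Those are different and narrower contrasts, but at a true AUC of 0.90 or 0.97 the net bias is downward over much or all of the range examined. This part of the objection stands.

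A reader might also call this incorporation bias. It is not: calprotectin is not a label criterion, and a cell count and a released protein are related but not identical quantities. Treating physicians do not know the calprotectin result, which prevents labels being influenced by it. That blinding does not remove a biological correlation between two readings from the same work-up.

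Excluding chemotherapy patients with an ANC below 1,000/mm³ removes one obvious cause of both markers being falsely low, but not the others. The number of patients labelled by WBC alone also depends on unknowns. If toxin detects 60% rather than 35% of inflamed patients, the share falls from about 50% to about 37%, or to about 20% with WBC at 30%/95%. A small share would make the problem small, and the plan does not provide for reporting it.

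**Conclusion.** The point holds as conditional dependence between the index test and one component of the reference standard, which no planned analysis separates. What is firm is that shared error raises the AUC relative to independent errors, and that independent label error lowers it. The net direction and size cannot be determined from the documents.

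Under the first set of assumed inputs, the planned AUC can lie 0.06 below to 0.10 above a true 0.75 (0.69 and 0.85), and 0.09 below to 0.03 above a true 0.90 (0.81 and 0.93). These are not values that one dataset could show: each belongs to a different assumed population, and one dataset gives one AUC against the planned label. The point does not invalidate the primary analysis. It calls for a cheap improvement: a second analysis showing how far the result depends on stool WBC.

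**What to change.** In Statistical Analyses, keep the planned ROC and add one pre-specified sensitivity ROC whose label ignores stool WBC entirely:

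- **Inflammatory:** toxin positive, or inflammation or ulceration on colonoscopy.
- **Non-inflammatory:** not in the first group, and either no inflammation on colonoscopy, or toxin negative with diet response, whatever the WBC count.
- **Left out of this ROC:** patients who meet neither definition.

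Do not drop patients merely because WBC was their only sign of inflammation. Some would meet the non-inflammatory definition above, so dropping them would let WBC filter that group again.

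Report the AUC with confidence interval and the cut-off beside those of the planned ROC, with the number of patients labelled by each criterion and by WBC alone. Interpret the efficacy conclusion in light of both. There should be no automatic replacement of the primary result: two AUCs on different subsets will almost always differ somewhat, and the WBC-free label has its own error.

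**Cost.** SAP wording and one more ROC on data already collected. Fewer patients are labelled: the SE of an AUC of 0.80 goes from 0.040 to about 0.047-0.053 if one third to one half of 61 inflammatory patients are WBC-only, so a 95% interval widens from about ±0.08 to about ±0.09-0.10 (1.96 × SE). Toxin and diet-response error remain, leaving the AUC about 0.01 to 0.04 low under the assumed inputs. If referral to colonoscopy depends on the stool result, a little dependence on WBC can persist through who is scoped.
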